1.0 HYPOTHESIS AND OBJECTIVES

Hypothesis

Ruxolitinib (also known as INCB018424), a JAK1/2 inhibitor, and pracinostat (a histone deacetylase inhibitor; HDACi) are effective and tolerable treatments for patients with myelofibrosis (MF). Combination of these agents in patients with MF can improve the overall clinical response to therapy without causing excessive toxicity.

Objectives

Primary:

- to determine the efficacy/clinical activity of the combination of ruxolitinib with pracinostat as therapy in patients with MF

Secondary:

- to determine the toxicity of the combination of ruxolitinib with pracinostat as therapy in patients with MF

Exploratory:

- to explore time to response and duration of response
- to explore changes in bone marrow fibrosis
- to explore changes in JAK2V617F (or other molecular marker) allele burden or changes in cytogenetic abnormalities

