8.0 STATISTICAL CONSIDERATIONS

This is a single-center phase II trial designed to assess the effect of ruxolitinib in combination with pracinostat in subjects with Primary, Post Polycythemia Vera, or Post Essential Thrombocythemia Myelofibrosis (PMF, post-PV MF, or post-ET MF).

The primary objective is to assess efficacy in terms of the objective response rate (i.e., complete and partial response, and clinical improvement by IWG-MRT) in patients with MF. Secondary objective is to determine the safety of the combination therapy in this population.

Primary Endpoint is the objective response rate (ORR), defined as a clinical improvement (CI), partial remission (PR), and complete remission (CR) according to the International Working Group (IWG) Criteria. All subjects meeting the eligibility criteria that have signed a consent form and have begun treatment will be evaluable for response.

A total of 25 patients will be enrolled from MDACC and patients will be registered through the Clinical Oncology Research System (CORE). The estimated accrual rate is 2-3 patients per month. Initially patients will receive ruxolitinib alone for the first 3 cycles, where 1 cycle is 28 days (i.e., 4 weeks). Then, starting from cycle #4, patients will receive the combination therapy of ruxolitinib with pracinostat.

The method of Thall, Simon and Estey [1995] will be used for futility and toxicity monitoring for this study. For futility monitoring, the primary endpoint of interest is the objective response (OR) rate at the end of 6 treatment cycles. Patients who drop off the study early due to any reason will be counted as failures (i.e., non-responders). The target response rate is 50% and the following futility stopping rule will be applied $\text{prob}\{p(\text{OR}) < 0.5\} > 0.95$, where $p(\text{OR})$ denotes the objective response rate, with a beta (1,1) prior distribution. That is, the treatment will be stopped if during the study we determine that there is more than 95% chance that the OR rate is less than 50%.

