For toxicity monitoring, we denote the probability of toxicity by $p(T)$, where toxicity is defined as Grade 3-4 clinically relevant non-hematologic toxicity or a serious adverse event that is at least possibly related to the study drug (Common Terminology Criteria for Adverse Events CTCAE version 4.0). We assume as a priori, $p(T) \sim \text{beta}(0.4, 1.6)$. We will stop treating patients if $\text{Pr}(p(T) > 0.20 | \text{data}) > 0.87$. That is, we will stop the trial for new patient enrollment if at any time during the study we determine that there is more than 87% chance that the toxicity rate is more than 20%. The OR rate and the toxicity will be monitored simultaneously using Bayesian stopping boundaries (Table 1) calculated based on beta-binomial distribution. Independence is assumed between OR and toxicity. Patients will be monitored in cohort size of 5, starting from the 5th patient. Multc Lean Desktop (version 2.1) was used to generate the futility/toxicity stopping boundaries and the operating characteristics table (Table 2).

Table 1: Stopping boundaries for OR and toxicity

Number of patients	Stop the trial if	Stop the trial if
--------------------	-------------------	-------------------

evaluated	there are this many OR patients	there are this many patients with toxicities
5	0	3-5
10	0-2	4-10
15	0-4	6-15
20	0-6	7-20

Table 2: Operating characteristics of the Bayesian futility and toxicity monitoring

True OR Rate	True toxicity Rate	Prob (stop the trial early)	Average sample size
0.3	0.1	0.69	15.7
	0.2	0.74	14.6
	0.3	0.84	12.4
	0.4	0.94	9.8
0.4	0.1	0.35	20.3
	0.2	0.46	18.6
	0.3	0.67	15.1
	0.4	0.88	11.3
0.5	0.1	0.13	23.1
	0.2	0.27	21.1
	0.3	0.56	16.8
	0.4	0.83	12.1
0.6	0.1	0.04	24.3
	0.2	0.2	22.1
	0.3	0.52	17.5
	0.4	0.82	12.5

Statistical Analysis Plan

Summary statistics will be provided for continuous variables. Frequency tables will be used to summarize categorical variables. The objective response rate (ORR) will be estimated along with the Bayesian 95% credible interval. Data from all subjects who receive any study drug will be included in the safety analyses. The severity of the toxicities will be graded according to the NCI CTCAE v4.0 whenever possible. We will follow standard reporting guidelines for adverse events. Safety data will be summarized by category, severity and frequency. The proportion of patients with AEs will be estimated, along with the Bayesian 95% credible intervals.

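### The safety objective is the combination, but no planned adverse-event proportion is specific to pracinostat-exposed patients, if study drug means both agents

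*Combined protocol and SAP*

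**What the plan says.** - **Objective.** Section 1.0 lists as secondary objective "to determine the toxicity of the combination of ruxolitinib with pracinostat as therapy in patients with MF". Section 8.0 repeats it: "Secondary objective is to determine the safety of the combination therapy in this population".
- **Regimen.** Section 8.0: "Initially patients will receive ruxolitinib alone for the first 3 cycles"; pracinostat is added from cycle 4. Under Section 5.0, ruxolitinib taken before enrolment is credited towards those three cycles, so some patients have a shorter on-study lead-in.
- **Safety analysis.** The Statistical Analysis Plan part of Section 8.0: "Data from all subjects who receive any study drug will be included in the safety analyses". The outputs are a summary by category, severity and frequency, and the proportion with adverse events with a 95% credible interval. Neither is split by treatment phase or limited to patients who took pracinostat.
- **Toxicity rule.** A toxicity is "Grade 3-4 clinically relevant non-hematologic toxicity or a serious adverse event that is at least possibly related to the study drug". No start point, window or required exposure is given. "The OR rate and the toxicity will be monitored simultaneously using Bayesian stopping boundaries", and Table 1 has one column of patients evaluated for both endpoints.
- **Response rule, for contrast.** Response is fixed at the end of six cycles, and "Patients who drop off the study early due to any reason will be counted as failures".

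**The concern.** A proportion over everyone who took either drug answers a question about the whole treatment sequence. The objective asks about the two drugs together. Under the pooled definition, an event in the ruxolitinib-only cycles counts as if it had occurred on the combination, which raises the rate. A patient who leaves before cycle 4 is in the denominator without having been at risk from the combination, which lowers it. A reader of the planned tables could not separate the two.

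The same silence affects the stopping rule. Two analysts could count different patients and different events at the same look, and an early look could hold little or no information about pracinostat.

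**Working it through.** **1. Which drugs are study drug?** The passages point both ways.
- Both agents: Section 5.0 has staff count study drug capsules and tablets, and pracinostat is described only as capsules. Section 5.6 collects unused study drug in each of the first seven cycles, which include the lead-in, and counts the ruxolitinib-only months as therapy in its laboratory schedule. Section 5.7 uses the plural.
- Pracinostat only: Section 3.2 lists pracinostat alone as investigational product and study medication, Section 5.0 uses study medication when describing how pracinostat is taken, and the toxicity definition is in the singular.

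The first reading is better supported. The second is possible.

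**2. The plan's own figures.** With the stated beta(0.4, 1.6) prior and the 0.20 and 0.87 limits, the toxicity boundaries at n = 5, 10, 15, 20 come out at 3, 4, 6, 7. With beta(1,1) and the 0.5 and 0.95 limits, the response boundaries are 0, 2, 4, 6. All match Table 1. At a true response rate of 0.5, the exact stopping probabilities for toxicity 0.1 to 0.4 are 0.131, 0.270, 0.563 and 0.835, against 0.13, 0.27, 0.56 and 0.83 in Table 2. The printed tables are correct for one constant toxicity rate per patient. What is open is which rate the count measures.

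**3. Size of the pooling effect (assumed counts).** Suppose N = 25 are treated, m = 20 start pracinostat, x = 6 of those have a toxicity on the combination, and L further patients have one in the lead-in only. The intervals use beta(0.4, 1.6), also an assumption, because Section 8.0 names no prior for the adverse-event intervals.

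| Set | Rate | 95% credible interval |
|---|---|---|
| Exposed, 6/20 | 30% | 13-49% |
| Any drug, L = 0, 6/25 | 24% | 10-41% |
| Any drug, L = 1, 7/25 | 28% | 13-45% |
| Any drug, L = 2, 8/25 | 32% | 16-49% |
| Any drug, L = 3, 9/25 | 36% | 18-53% |

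The pooled rate exceeds the exposed rate when (x + L)/N > x/m, that is L > x(N - m)/m = 6 × 5/20 = 1.5. So the direction changes between one and two lead-in-only patients. With beta(1,1) the intervals move slightly: 6/20 gives 15-52%, 6/25 gives 12-44% and 9/25 gives 20-56%.

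**4. Timing of the first toxicity look.** Section 8.0: "The estimated accrual rate is 2-3 patients per month". With the first patient at month 0 and uniform accrual, the 5th enrols at 4/3 = 1.3 to 4/2 = 2.0 months. A patient with no prior ruxolitinib reaches day 1 of cycle 4 after 3 × 28 = 84 days, or 84/30.44 = 2.8 months. If patients count from enrolment and none had prior ruxolitinib, the first look contains no pracinostat exposure. The chance of reaching the boundary of 3 in 5 is then 0.1% to 0.9% at an assumed lead-in toxicity rate of 5% to 10%, against 31.7% if all five were at risk at a combination rate of 40%.

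**5. What waiting for exposure would cost.** Patients past k cycles when the 25th enrols number 25 - rate × k × 28/30.44. For k = 3 this is 19.5 at 2 per month and 16.7 at 3 per month; for k = 4 it is 17.6 and 14.0. With a full lead-in and no drop-outs, an exposure-based look at 20 would therefore fall after accrual, and the look at 15 might. Toxicity-only stopping at a true 40% is 0.81 with all four looks, 0.71 without the look at 20, and 0.64 with looks at 5 and 10 only. At a true 30% the figures are 0.51, 0.42 and 0.37.

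**The case against.** - **The term may mean pracinostat.** If so, the safety set is already the exposed set and most of the main point falls away. This stands, so the point is conditional and the term must be defined.
- **An all-treated set is standard, and the lead-in is a deliberate part of the regimen.** This also stands. A reader might infer that the safety set is itself an error. It is not: it is a sound overall summary. What is missing is an estimate matched to the combination objective.
- **Nothing bars a split by phase, and attribution is recorded for each event (Section 7.2, on expedited reporting).** True, and it makes the fix cheap. But no split is planned, and attribution does not correct the denominator.
- **The toxicity rule may be tied to the six-cycle response evaluation through simultaneous monitoring and the shared column.** Possible, but not stated. Even then, three of the six cycles are ruxolitinib alone, and patients who left before cycle 4 would still be counted as evaluated, as response failures. The recording windows in Sections 7.1 and 7.2 say when events are captured; they do not refer to cycle 4 or to the rule.
- **The numbers are assumed.** They are. The intervals overlap heavily, and crediting prior ruxolitinib lessens both the pooling effect and the timing effect.

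**Conclusion.** If study drug covers both agents, no planned output estimates the toxicity of the combination, which is the stated objective. This should be corrected. The example (24% to 36% against 30%) rests on invented counts and shows only that the gap can go either way.

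Three stronger readings are tempting. One is that the plan understates, or overstates, combination toxicity: the documents give neither the share who never start pracinostat nor a lead-in toxicity rate, so no direction can be claimed. Another is that Tables 1 and 2 are wrong: they reproduce. The third is that the stopping rule must exclude lead-in events or wait for exposure: waiting costs power during accrual (0.81 to 0.71 or 0.64 at 40% toxicity), and dropping lead-in toxicity from a safety rule is itself a trade-off.

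The secondary point is narrower. The rule does not say who counts as evaluated for toxicity, and a first look counted from enrolment may hold no pracinostat exposure. That rests on the planned accrual rate and on patients without prior ruxolitinib.

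**What to change.** In Section 8.0:

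1. Define study drug for the safety analyses and for the toxicity rule.
2. Keep the all-treated set as the overall safety summary. As the estimate for the combination objective, report adverse-event proportions with 95% credible intervals among patients with at least one pracinostat dose, counting events with onset or worsening on or after that dose. State the prior. Tabulate lead-in events separately.
3. State which patients count as evaluated in the toxicity column of Table 1. The boundaries do not change. Rerun Table 2 if the toxicity denominator differs from the response one.

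The evaluation time, and whether lead-in events also count towards stopping, are left to the sponsor to weigh against the timing of the looks.

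The cost of item 2 is one extra set of adverse-event tables and a smaller denominator. In the example the interval widens from about 31 points (41.1 - 10.0, for 6/25) to about 37 (49.2 - 12.6, for 6/20). The split needs pracinostat start dates and event onset or worsening dates, which the treatment diaries and routine event recording should supply. Items 1 and 3 cost wording and, at most, one rerun of Table 2.

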5.0 TREATMENT PLAN

On this study 4 weeks of therapy is considered one cycle of therapy. Ruxolitinib and pracinostat will be given orally in an outpatient setting. Ruxolitinib will be given continuously daily in 28-day cycles. Patients will receive ruxolitinib alone for the first 3 months, and then pracinostat will be added. Ruxolitinib provides maximum benefit usually within 3 months, therefore we add another agent to ruxolitinib after those initial 3 months, in order not to compromise benefit of ruxolitinib with some new side effect from additional medication (pracinostat in this case). Starting dose of ruxolitinib will be based on patients' platelet count, as per standard practice: 15 mg twice a day (BID) for patients with baseline platelet counts of $100\text{--}200 \times 10^9/\text{L}$ and 20 mg BID for those with baseline platelet counts $>200 \times 10^9/\text{L}$. For patients with platelet counts of $50\text{--}99 \times 10^9/\text{L}$, gradual up-titration from a starting dose of 5 mg BID is recommended. Dose of ruxolitinib may be increased or decreased at the discretion of the treating physician prior to initiation of pracinostat (see section 5.1). Patients who started ruxolitinib before enrollment into this study, will have the time they have been on ruxolitinib therapy counted toward the 3 cycles of ruxolitinib monotherapy, as per protocol. When a dosage change of the Ruxolitinib is indicated (except for holding therapy due to toxicity) patients will continue taking their previously prescribed dosing level until the new supply of Ruxolitinib is available for use by the patient.

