Duration of response: Duration of response is defined as the date at which the subject's objective status is first noted to be a CR, PR or CI to the date of progression (no longer meeting criteria for either CR, PR or CI) is documented (if one has occurred). Patients who continue to respond as of the data cut-off date will be censored as of the date of their last assessment documenting continued response.

Time to response: The time to response is defined as the time from study registration to the first date at which the subject's objective status was classified as a response (CR, PR or CI). In subjects who do not achieve a response, time to response will be censored at the subject's last evaluation date.

The distribution for each of these event-time variables (duration of response and time to response) will be estimated by Kaplan-Meier curves.

Anemia: Descriptive statistics will be used to explore improvements in anemia and transfusion dependence. The following outcomes will be summarized: mean changes in hemoglobin at monthly intervals. The proportion of transfusion independent patients not requiring transfusions on study who experience an increase of 2 g/dL in their hemoglobin relative to baseline, the proportion of transfusion dependent patients (defined as requiring a transfusion of 2 units PRBCs monthly for 3 months (12 weeks) prior to starting the trial) who become transfusion independent (not requiring a transfusion of PRBCs over a period of 3 months (12 weeks) while on study), the proportion of transfusion dependent patients who become transfusion independent and have a 1 g/dL increase in hemoglobin relative to baseline, and the proportion of transfusion independent patients requiring a transfusion while on study.

JAK2V617F Allele burden: Change in JAK2V617 allele burden from baseline to each visit where it is measured.

Correlative Studies: Descriptive statistics will be applied to the analysis of these findings.

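### Time to response runs from registration on a single curve, so it counts responses that precede pracinostat and mixes patients with different pracinostat exposure

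*Combined protocol and SAP*

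**What the plan says.** In the combined protocol and SAP, section 8.0 fixes the time origin in one sentence: "The time to response is defined as the time from study registration to the first date". The event that stops the clock is any CR, PR or CI, with no condition that pracinostat has started. For patients who never respond, "time to response will be censored at the subject's last evaluation date". The analysis is a single estimate: "The distribution for each of these event-time variables (duration of response and time to response) will be estimated by Kaplan-Meier curves".

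Treatment comes in two stages. Section 8.0 has ruxolitinib alone for three 28-day cycles; then, "starting from cycle #4, patients will receive the combination therapy of ruxolitinib with pracinostat". Section 5.0 gives the reason for the delay: "Ruxolitinib provides maximum benefit usually within 3 months".

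Patients who have already been on ruxolitinib for less than 3 months may enrol (section 4.0, exclusion criterion 1). Under section 5.0 they "will have the time they have been on ruxolitinib therapy counted toward the 3 cycles of ruxolitinib monotherapy".

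Section 5.6 schedules formal response assessments after cycle 3, after cycle 6 and then every 6 cycles. Spleen size and the symptom score are recorded more often in the early cycles. Section 1.0 lists time to response among the exploratory objectives. No section sets a second time origin, separates responses before and after cycle 4, or splits the curve by prior ruxolitinib.

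**The concern.** The primary objective is the activity of the combination, yet the response clock takes no account of when the combination begins. Two consequences follow.

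First, a patient who meets CI on ruxolitinib alone is an event before taking any pracinostat. That event is then spent: a further gain after pracinostat is added, such as the blood-count improvement hoped for in section 2.4, cannot enter the curve.

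Second, registration is not the same point in treatment for everyone. For a ruxolitinib-naive patient it sits 12 weeks before pracinostat. For a patient with nearly 3 months of prior ruxolitinib it sits almost at the first pracinostat dose. One median over both groups has no single meaning in terms of pracinostat exposure, and a reader cannot tell from it whether responses came before or after pracinostat. Duration of response starts at first response, so it too can begin in the lead-in.

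**Working it through.** The documents state no figure for time to response, so there is none to reproduce. The check is timeline arithmetic.

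**Inputs.** Cycle length 28 days and 3 lead-in cycles (section 8.0); prior ruxolitinib credited to the lead-in (section 5.0); prior use under 3 months (section 4.0); assessments after cycles 3, 6 and 12 (section 5.6).

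**Assumptions.** No cycle delays, and no gap between registration and the first on-study dose. Prior use of 83 days stands for the upper end.

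**Step 1: ruxolitinib-naive patients.** Lead-in = 3 × 28 = 84 days. The assessments fall on days 84, 168 and 336.

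| First response recorded | Days from registration | Days from first pracinostat | Lead-in share |
|---|---|---|---|
| After cycle 3 | 84 | 0 (none taken yet) | 84/84 = 100% |
| After cycle 6 | 168 | 168 − 84 = 84 | 84/168 = 50% |
| After cycle 12 | 336 | 336 − 84 = 252 | 84/336 = 25% |

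**Step 2: patients with d days of prior ruxolitinib.** On-study lead-in = 84 − d. For a response on day 168 after registration, time on the combination = 168 − (84 − d) = 84 + d.

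| d | On-study lead-in | Days on combination at day 168 | Lead-in share of 168 days |
|---|---|---|---|
| 0 | 84 | 84 | 50% |
| 28 | 56 | 112 | 33% |
| 56 | 28 | 140 | 17% |
| 83 | 1 | 167 | 1% |

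The same recorded time therefore covers exposures that differ by 167 − 84 = 83 days, about 12 weeks. The discrepancy can also be read in reverse. A response after exactly 84 days on the combination is recorded at 168 − d days, which is 168, 140, 112 or 85 days for the same four patients.

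**Step 3: how much of the summary could be lead-in.** The documents do not give the share s of responders first recorded after cycle 3. Suppose, for illustration only, that all patients are ruxolitinib-naive and every response is recorded after cycle 3 or cycle 6. Mean time to response among responders is 84s + 168(1 − s), and the lead-in share of it is 84 divided by that mean.

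| s | Mean (days) | Lead-in share |
|---|---|---|
| 0% | 168 | 50% |
| 25% | 147 | 57% |
| 50% | 126 | 67% |
| 75% | 105 | 80% |
| 90% | 92.4 | 91% |

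Later first responses would lower these shares, as the cycle 12 row in step 1 shows.

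**Step 4: does anything else in the design depend on this?** No. The boundaries in Table 1 and all 16 rows of Table 2 reproduce within rounding from the stated priors and cut-offs, with looks at 5, 10, 15 and 20 patients and a maximum of 25. None of them uses time to response.

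**The case against.** The strongest defence is that study treatment is a sequence, ruxolitinib and then both drugs, and that registration is a proper origin for it. Section 8.0 treats patients as evaluable once treatment begins and judges futility after 6 cycles, lead-in included. A registration origin fits that framework, keeps every enrolled patient and avoids selection at cycle 4. This stands, and it is why the registration curve should be kept.

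Three stronger readings are tempting, and the documents do not support them.

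- A reader might infer that the curve largely measures the lead-in. The statement about maximum ruxolitinib benefit within 3 months, and the earlier pracinostat study in section 2.3 (2 IWG responses in 22 patients, both anemia), make early responses plausible. Neither gives an IWG response rate by week 12 on ruxolitinib. Section 5.0 also allows for delayed responses. The number of enrolled patients with prior ruxolitinib is unknown and could be zero.
- A reader might infer that the plan credits pracinostat with these responses. Section 8.0 attributes nothing to either drug.
- A reader might take the exploratory objective to be time to response on the combination. Section 1.0 does not say so for this objective; the combination is named in the primary and secondary objectives.

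It is also fair to say that the cycle 3 assessment lets lead-in responses be picked out for ruxolitinib-naive patients. But the plan does not say that anyone will do so, and reading the curve at week 12 does not work for pre-treated patients, whose pracinostat starts earlier on that clock.

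**Conclusion.** The point holds as one of interpretation. As defined, the curve counts responses that precede pracinostat as events, and the same time from registration can reflect pracinostat exposure differing by up to about 12 weeks (84 against about 167 days for a response on day 168). Both facts follow from the text and rest only on undelayed 28-day cycles and the crediting rule in section 5.0. How far the reported median is affected cannot be settled from the documents, because it depends on the share of responses before cycle 4 and on how many patients enrol already on ruxolitinib. The endpoint is exploratory and descriptive in a single-arm trial of 25 patients. The primary response rate, the sample size and the stopping rules are untouched. The change is still worth making, because without it a trial of the combination cannot show on this endpoint whether responses followed pracinostat.

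**What to change.** Amend the time-to-response paragraph in section 8.0 as follows.

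- Keep the curve from registration, labelled as describing the whole sequence of ruxolitinib followed by the combination.
- Add time to response from the first pracinostat dose (cycle 4 day 1), among patients not already in CR, PR or CI on that date. Judge response against the pretreatment IWG baseline required by the footnote in section 6.0. A new baseline at cycle 4 would contradict that footnote. State which measurement counts as pretreatment for patients who enrol on ruxolitinib.
- List responses already present at cycle 4 day 1 as lead-in responses, and report patients who leave before cycle 4 beside the added curve.
- Show both summaries by prior ruxolitinib use (none, or some).

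Moving the origin back to the first ruxolitinib dose is not recommended as a replacement. For pre-treated patients it would add time before enrolment with no protocol assessments, which brings in delayed entry.

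The cost is SAP wording and a little analysis. The assessments are already scheduled, dosing is recorded in diaries, and crediting prior ruxolitinib already requires its start date. The downside is that the added curve rests on a smaller, selected subset of at most 25 patients, so it should be presented as descriptive.

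### Kaplan-Meier for time to response censors non-responders who left the study together with those still on it, so the curve overstates the chance of response whenever a response follows a departure

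*Combined protocol and SAP*

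**What the plan says.** Three statements in section 8.0 bear on this point.

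- **Time to response.** The clock starts at registration: "The time to response is defined as the time from study registration to the first date at which the subject's objective status was classified as" CR, PR or CI. For everyone else the rule is: "In subjects who do not achieve a response, time to response will be censored at the" last evaluation date. It does not depend on why evaluation ended.
- **Estimator.** "The distribution for each of these event-time variables (duration of response and time to response) will be estimated by Kaplan-Meier curves". No competing-risk method is named anywhere in the document.
- **ORR denominator.** "All subjects meeting the eligibility criteria that have signed a consent form and have begun treatment will be evaluable for response". A treated, eligible patient who leaves without responding therefore stays in the denominator.

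Section 5.7 ends study treatment for lack of effect, for certain adverse events and for death, among other reasons. Section 5.0 lets patients with clinical benefit continue for up to 4 years unless progression or toxicity intervenes. Section 5.6 schedules response assessment after cycles 3 and 6 and then every 6 cycles. Section 1.0 lists time to response as an exploratory objective.

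**The concern.** Kaplan-Meier treats a censored patient as having the same future chance of response as those who remain under observation. That is reasonable for a non-responder still on study when the data are cut. It is not reasonable for one who has died, progressed, or gone off study because the treatment did not work or was not tolerated: no later on-study response can be recorded for that patient. These exits are competing events, and leaving for lack of effect is directly tied to the outcome.

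Two outputs are at stake. The plotted cumulative response, or a median taken from it, could look better than the trial's experience. The same report could also show a curve and an ORR that differ for the same 25 patients, because patients who left are fully counted in one and censored in the other.

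**Working it through.** **Plan's own figures.** The plan gives no number for time to response. Its only design figures are the stopping boundaries (Table 1) and operating characteristics (Table 2). Both recompute from the stated priors, cut-offs and looks at 5, 10, 15 and 20 patients. For example, at a true OR rate of 0.5 and toxicity rate of 0.2, the exact early-stopping probability is 0.270 and the average sample size 21.06, against the stated 0.27 and 21.1. None of these figures uses the time-to-response curve.

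**Inputs.** From the documents: 25 patients, and assessments after cycles 3 and 6 and then every 6 cycles. Assumed, because the documents give no dropout rate: all response counts and departure counts below.

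**Step 1: one interval.** Suppose 4 patients respond at cycle 3 and 8 at cycle 6, so 12/25 = 48%. Let *d* non-responders leave after the cycle 3 assessment and before the cycle 6 assessment. Of the 25, 21 have not responded after cycle 3, so 21 − *d* are at risk at cycle 6:

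1 − KM = 1 − (21/25) × (21 − *d* − 8)/(21 − *d*)

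| *d* | Calculation | 1 − KM | Cumulative incidence |
|---|---|---|---|
| 3 | 1 − 0.84 × 10/18 | 53% | 48% |
| 5 | 1 − 0.84 × 8/16 | 58% | 48% |
| 8 | 1 − 0.84 × 5/13 | 68% | 48% |

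The mechanism is visible with *d* = 5. Kaplan-Meier passes the weight of the 5 who left to the 16 who stayed, so each cycle 6 response counts (1/25) × (21/16) = 5.25% instead of 4%. Then 16% + 8 × 5.25% = 58%. In all three rows the curve crosses 50% at cycle 6, so a median would be read there although fewer than half of the patients have responded.

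**Step 2: constant hazards.** Fix the true cumulative incidence of response at 50% by cycle 6, and let a fraction *L* leave without response by then. With constant competing hazards:

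1 − KM = 1 − (0.50 − *L*)^(0.50/(0.50 + *L*))

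- *L* = 10%: 1 − 0.40^0.833 = 53%
- *L* = 20%: 1 − 0.30^0.714 = 58%
- *L* = 30%: 1 − 0.20^0.625 = 63%

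**Step 3: longer follow-up.** Take 13 responders (52%): 6, 4, 2 and 1 at cycles 3, 6, 12 and 18. Departures are placed after the cycle 3, 6 and 12 assessments.

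- 0, 1 and 2 leave: 1 − (19/25)(15/19)(12/14)(9/10) = 53.7%
- 2, 4 and 3 leave: 1 − (19/25)(13/17)(7/9)(3/4) = 66.1%
- 3, 5 and 4 leave: 1 − (19/25)(12/16)(5/7)(0/1) = 100%, because the last patient at risk responds

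Cumulative incidence is 52% in all three. The gap widens as the risk set empties.

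**Step 4: direction.** When departures are the only censoring, 1 − KM is never below the cumulative incidence. The two are equal if no response follows a departure.

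**The case against.** The strongest reply is that little hangs on this curve. Time to response is exploratory in a 25-patient single-arm trial. The plan's estimate of the chance of response is the ORR with its credible interval, and section 8.0 promises neither a median nor a 1 − KM percentage. All of that stands, and it limits the weight of the point.

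The size is also uncertain. Section 5.0 aims for at least 6 months of treatment, and section 5.7 asks for 3 to 6 cycles before removal for lack of effect. Departures may therefore cluster at or after the cycle 6 assessment, when fewer responses remain to be inflated. The 68% row needs 8 of 25 patients (32%) to leave between two assessments. In the earlier pracinostat study in MF (section 2.3), 21 of 22 patients went off study, 9 of them for lack of response and 6 for progression. That study did not use this combination, so it shows that such exits occur but supplies no rate for this trial.

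A reader might infer two stronger points that the documents do not support.

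- **That the plan contradicts its own drop-off rule.** The rule reads "Patients who drop off the study early due to any reason will be counted as failures (i.e., non-responders", but it follows "For futility monitoring, the primary endpoint of interest is the objective response (OR) rate at the end of 6 treatment cycles" and belongs to that monitoring. It does not govern time to response. The mismatch is between the curve and the ORR denominator: an inconsistency between two analyses.
- **That any patient who stops treatment can no longer respond.** Sections 5.1 and 5.2 allow one drug to be stopped while the other continues, and such a patient may still be assessed and respond. Stopping one drug is not in itself the competing event.

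**Conclusion.** The point holds as a conditional bias with a known direction. Censoring all non-responders alike makes 1 − KM, and any median read from it, too high as a statement of the cumulative chance of response whenever a response follows a departure. The bias is nil if none does, and censoring non-responders still on study at data cut-off is proper.

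The direction is certain; the size is not. In the assumed one-interval case the excess is 5, 10 or 20 percentage points over 48% (3, 5 or 8 departures). Under constant hazards it is about 3 to 13 points over 50% at cycle 6 (10% to 30% leaving). These are illustrations of scale, not forecasts. The ORR, the stopping boundaries and the sample size do not change. The correction is worth making because it needs no new data and brings the curve into line with the ORR denominator.

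**What to change.** Replace the censoring and estimator wording for time to response in section 8.0 so that it says the following:

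- Time to response is estimated by a cumulative incidence function (Aalen-Johansen).
- The competing event is the end of response follow-up on study without a response: off study for any reason, progression or death.
- Patients who stop one drug but are still being assessed for response stay in the risk set.
- Only non-responders still on study at data cut-off are censored.
- Median time to response is described among responders and labelled as such, beside the ORR.

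The cost is a short change of wording and standard software. The date and reason for ending response follow-up must be available for each patient in the analysis file. The downside for the sponsor is that the reported curve becomes less favourable, by an amount that depends on how many patients leave before later responses occur.
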